10.5.4. Sessions 4-9 (by telephone)

These six sessions take place at Days 28, 42, 56, 90, 120 and 180 (all \pm 7 days) post-hospital discharge.

The ALN will contact the participant by telephone as described in section 10.6. All sessions last less than 15 minutes.

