3 TRIAL DESIGN

3.1 GENERAL DESIGN

Multicentre randomised controlled pilot trial of FIT+TAU (intervention group) vs TAU alone (control group).

[figure not shown]

Figure 1: Flow of participants' progression through the MIRAGE pilot trial.

TAU comprises of one brief MI-based session given in hospital by the ALN. All participants should receive TAU. Due to local hospital practices, participants may have received TAU prior to being approached about this study, prior to giving informed consent, or prior to completing the baseline measures and being randomised. The FIT intervention comprises of one session given face-to-face to participants before discharge from hospital, a second session given, if possible, face-to-face to patients in an outpatient clinic or via telephone and then a further seven sessions delivered by telephone over a period of 6 months.

All participants will be scheduled for follow-up at 28 (± 7), 90 (± 7) and 180 (± 14) days post-baseline. Figure 1 shows participants' progression through the study and time points they receive the FIT intervention (if allocated to TAU + FIT) and their follow-up assessments.

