5.2 ANALYSIS OF PILOT OUTCOME MEASURES

In addition to the summary statistics detailed in section 5.1, the following data will be summarised:

- Time to recruit total study sample
- Number (percentage) of participants who completed TAU before recruitment or after recruitment but before baseline assessment, and number (percentage) of participants who completed TAU post-baseline assessment, in total and by site
- Time elapsed, by allocated group, of:
 - baseline assessment to randomisation
 - baseline to 28 (± 7) day assessment
 - baseline to 90 (± 7) day assessment
 - baseline to 180 (± 14) day assessment
- Number of assessments completed within the 28, 90 and 180-day assessment windows
- Acceptability of and adherence of FIT programme:
 - Number (percentage) of participants in the intervention group who completed:
 - all FIT sessions
 - ≥ 2 FIT sessions
 - FIT session 1 along with at least one of FIT session 2 or FIT session 3
 - each of the nine FIT sessions
- Number (percentage) of participants re-hospitalised

- Number (percentage) of participants who relapsed to alcohol use.
- Time elapsed between randomisation and start of the FIT sessions
- Number (percentage) of FIT sessions delivered within the specified time frame (see Figure 1 for specified time frames)
- Number (percentage) of participants who attended at least four FIT sessions before the 28 day assessment
- Number (percentage) of participants who attended at least seven FIT sessions before the 90 day assessment
- Number (percentage) of participants who attended at least nine FIT sessions before the 180 day assessment
- Time elapsed between the last FIT session participant attended and the 180 day assessment
- Number who attended final fit session after 180 day assessment
- Feasibility of using the proposed patient- and clinician-reported outcome measures. For each outcome measure we will report (by allocated group and overall):
 - Number (percentage) of participants who completed all items of the outcome measure (if relevant)
 - Number (percentage) of participants with a valid total score for each outcome measure, allowing for appropriate imputation methods if available.

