APPENDIX A: PLOTS AND TABLES

Examples of potential tables and plots to be used in the statistical analysis report.

*TAU may be completed before recruitment, post recruitment or after baseline assessment.

Figure 2: CONSORT diagram of participant flow through the MIRAGE Pilot Trial

Table 3: Number of participants who completed TAU before recruitment, post recruitment or after baseline assessment

Site	Before recruitment N (%)	Post recruitment but before baseline assessment N (%)	Post baseline assessment N (%)
1			
2			
3			
4			
Total			

Table 4: Number of assessments completed within the scheduled 28, 90, and 180-day assessment windows

Assessments Completed	TAU N (%)	FIT + TAU N (%)	ALL N (%)
28-day window (± 7 days)			
90-day window (± 7 days)			
180-day window (± 14 days)			

Table 5: Time differences between key events

Time Elapsed (days) Between	TAU Mean (SD) [range]	FIT + TAU Mean (SD) [range]	ALL MEAN (SD) [range]
Baseline and randomisation			
Randomisation and start of the FIT sessions*	N/A		
Randomisation and 28 (± 7) days post baseline assessment			
Randomisation and 90 (± 7) days post baseline assessment			
Randomisation and 180 (± 14) days post baseline assessment			
Last FIT session attended and 180 (± 14) days post baseline assessment*	N/A		

* FIT participants only

Table 6: Number of participants attending the recommended number of FIT sessions before the assessments

Number of Participants	FIT + TAU N (%)
Attended ≥ 4 FIT sessions before 28 (± 7) day assessment	
Attended ≥ 7 FIT sessions before 90 (± 7) day assessment	
Attended ≥ 9 FIT sessions before 180 (± 14) day assessment	
Attended final FIT session after 180 (± 14) day assessment	

Table 7: Acceptability and adherence to the FIT intervention

Fit Session	Completed total N (%)	Completed within specified timeframe N (%)	Cumulative total of completion N (%)	Cumulative total of completion within specified timeframe N (%)
1 (in-patient)				
2 (face-to-face or telephone)				
3 (telephone)				
4 (telephone)				
5 (telephone)				
6 (telephone)				
7 (telephone)				
8 (telephone)				
9 (telephone)				
Total				

Table 8a: Completeness of proposed primary and secondary outcomes

Outcome	Time Point	TAU			FIT + TAU			All		
		Number (%) of Participants			Number (%) of Participants			Number (%) of Participants		
		Attended Visit	Completed All Items	With Valid Score	Attended Visit	Completed All Items	With Valid Score	Attended Visit	Completed All Items	With Valid Score

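### The 4/7/9-session counts in SAP Table 6 set sessions timed from discharge against visits timed from baseline, so they understate adherence if read as adherence

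*SAP*

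**What the plan says.** SAP 5.2 lists, among the pilot outcome summaries, "Number (percentage) of participants who attended at least four FIT sessions before the 28 day assessment", a matching count of seven sessions for day 90, and "Number (percentage) of participants who attended at least nine FIT sessions before the 180 day assessment". Appendix A lays these out in Table 6, under the title "Number of participants attending the recommended number of FIT sessions before the assessments", with the rows "Attended ≥ 4 FIT sessions before 28 (± 7) day assessment", "Attended ≥ 7 FIT sessions before 90 (± 7) day assessment" and "Attended ≥ 9 FIT sessions before 180 (± 14) day assessment". A fourth row counts participants whose final session came after the 180-day visit. The word *recommended* appears in the table title but not in the SAP 5.2 list.

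The two sets of dates have different starting points:

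- **Visits.** SAP 3.1: "All participants will be scheduled for follow-up at 28 (± 7), 90 (± 7) and 180 (± 14) days post-baseline".
- **Sessions 4 to 9.** Protocol 10.5.4: "These six sessions take place at Days 28, 42, 56, 90, 120 and 180", each ±7 days and counted from hospital discharge.
- **Order of events.** Protocol 10.1.3 places randomisation after all baseline data collection. Protocol 10.5.1 places session 1 between randomisation and discharge. Discharge therefore cannot precede baseline.

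Protocol 14 shows both clocks together: the end-of-trial visit is timed from baseline and the last FIT session from discharge.

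**The concern.** Sessions 4, 7 and 9 carry the same day numbers as the three visits, but their clock starts later. Each benchmark session is therefore nominally due on or after the visit that it is supposed to precede. A participant who attends every session on its nominal date misses all three rows.

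Adherence to FIT is part of primary objective 1. A low percentage against a number labelled as recommended invites the reading that participants did not engage, when some or most of the shortfall comes from the calendar. The shortfall grows with the time between baseline and discharge, so sites with different lengths of stay could also appear to differ in delivery when they do not.

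**Working it through.** **Inputs.** Let g be the number of days from baseline to discharge. The documents give no value, so g is an assumption and is shown over a range. Timings after discharge, from Protocol 10.5.1 to 10.5.4:

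- session 1: before discharge
- session 2: within 10 days
- session 3: day 14 (±4)
- sessions 4 to 9: days 28, 42, 56, 90, 120 and 180 (all ±7)

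Visits are on days 28 (±7), 90 (±7) and 180 (±14) after baseline.

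**Reproducing 4/7/9.** On nominal dates, session 4 is on or before the day-28 visit if g + 28 ≤ 28, that is, only if g = 0. Sessions 7 and 9 give the same condition. So 4, 7 and 9 are obtained only when discharge falls on the baseline day and a same-day session counts as before the visit.

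**Nominal count strictly before each visit.**

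- Day 28: session 3 counts if g + 14 < 28, so g ≤ 13. Session 4 never counts. The total is 3 for g = 0 to 13 and 2 at g = 14. It is 1 from g = 18 if session 2 is held on its last permitted day (18 + 10 = 28).
- Day 90: session 6 counts if g + 56 < 90, so g ≤ 33. Session 7 never counts. The total is 6.
- Day 180: session 8 counts if g + 120 < 180, so g ≤ 59. Session 9 never counts. The total is 8.

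The result is 3, 6 and 8 for gaps of 0 to 13 days.

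**What the windows allow.** Take the earliest permitted session and the latest permitted visit:

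- four sessions: g + 21 < 35, so g ≤ 13
- seven sessions: g + 83 < 97, so g ≤ 13
- nine sessions: g + 173 < 194, so g ≤ 20

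With everything in window, the first two rows cannot be met from g = 14, nor the third from g = 21.

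**How often a fully adherent participant meets each row.** Suppose every session is attended, and session and visit dates are independent and uniform within their windows. Sessions 4, 7 and 9 always come after the sessions numbered below them, because the windows do not overlap at those points. Each row is then met exactly when that session precedes the visit.

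- Days 28 and 90 (both windows ±7): P = (14 − g)² / 392 for g ≤ 14, and 0 beyond.
- Day 180 (session ±7, visit ±14): P = (14 − g) / 28 for g ≤ 7, and (21 − g)² / 784 for g from 7 to 21.

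| g (assumed) | ≥4 before day 28 | ≥7 before day 90 | ≥9 before day 180 |
|---|---|---|---|
| 0 | 196/392 = 50% (47%) | 50% (47%) | 14/28 = 50% (48%) |
| 3 | 121/392 = 31% (29%) | 31% (29%) | 11/28 = 39% (38%) |
| 7 | 49/392 = 12.5% (12%) | 12.5% (12%) | 7/28 = 25% (24%) |
| 14 | 0% (0%) | 0% (0%) | 49/784 = 6% (6%) |

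Figures in brackets count whole days and require the session to fall strictly before the visit day.

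**The other description of the schedule.** Protocol 5.2 describes sessions 4 to 9 as monthly, which does not match the days listed in 10.5.4. Taking 30-day months and g = 0, a series starting on day 28 (28, 58, 88, 118, 148, 178) gives 3, 6 and 9 sessions strictly before the visits. From g = 2 this becomes 3, 5 and 8, because 88 + 2 = 90 and 178 + 2 = 180. A series starting on day 44 gives 3, 5 and 8 at g = 0. Neither version yields 4, 7 and 9.

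**The case against.** The strongest reply is that Table 6 is not the adherence table. SAP 5.2 lists adherence under its own bullet (all sessions, at least two, session 1 plus session 2 or 3, each of the nine). Table 7, whose title names acceptability and adherence, reports completion both overall and within each session's own time frame, so a participant treated on schedule is credited there. The SAP also anticipates the overlap. SAP 3.4.2 counts visits held before sessions 4, 7 and 9, and separately the number of sessions completed before each follow-up. Table 6's fourth row counts final sessions after the 180-day visit. The 4/7/9 counts also have a legitimate use: they show how much of the course had been received when each outcome was measured. Finally, Appendix A offers only example tables.

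Most of this stands, and it limits the point. A reader might infer that Table 6 scores a perfectly adherent participant as a failure. The documents do not support that: no pass or fail rule is attached to these rows, and the windows let some adherent participants reach 4, 7 and 9 when the gap is short. A reader might also infer that 3, 6 and 8 are the correct fixed thresholds. They are not, because the day-28 count falls below 3 from a 14-day gap.

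The reply does not remove the label. Table 6 calls 4, 7 and 9 the recommended number before the assessments, and neither schedule in the protocol text recommends that. An exposure count is sound as an exposure count. Under this title it will be read as a target that participants missed.

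**Conclusion.** The mismatch follows directly from the documents. On nominal dates 3, 6 and 8 sessions are due strictly before the visits for gaps of 0 to 13 days, against a stated 4, 7 and 9. If the rows are read as adherence, about half of fully adherent participants would miss each one at a gap of 0 days. At 7 days about 88%, 88% and 75% would miss them, and at 14 days 100%, 100% and 94%.

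The nominal counts need only the protocol's listed days. The percentages rest on an assumed gap and on independent uniform dates, so they illustrate scale and do not predict the result. SAP Figure 1, to which SAP 5.2 refers for the session time frames, is not reproduced in the text available and could not be checked.

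It would be wrong to infer that the decision to progress is at risk. The adherence criterion in SAP 5.5 is session 1 plus session 2 or 3, and 4/7/9 plays no part in it. Table 7 is likewise unaffected. The consequence is a misleading descriptive figure on a component of primary objective 1, which should be corrected.

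**What to change.** 1. In SAP 5.2 and Table 6, report as the adherence measure the number of sessions attended out of those due by each participant's actual assessment date, with due dates counted from that participant's discharge date. This handles any length of stay, which fixed thresholds of 3, 6 and 8 would not. State whether a session becomes due on its nominal day or when its window closes. The second choice avoids counting as missed a session that is still in window at the visit.
2. If the 4/7/9 counts are kept, retitle them as FIT sessions received before assessment (exposure), remove the word *recommended*, and present them beside the session-order counts from SAP 3.4.2.
3. Reconcile the monthly description of sessions 4 to 9 in Protocol 5.2 with the days listed in Protocol 10.5.4. Which is intended is for the trial team, and no change to the treatment schedule is proposed.

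The cost is a few lines of SAP text, one table caption and one derived variable. The discharge date is already needed for Table 7's within-timeframe columns, so the change adds no data collection.

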17.4. Outline of statistical analyses

Trial science outcomes, such as recruitment and retention rates, completeness of outcome measures at each follow-up, will be presented as frequencies and percentages (with confidence intervals), overall and by allocated group where relevant. The timing and frequency of missing outcome data will be summarised. Individuals lost to follow-up will be compared to those who complete the pilot study to identify any potential bias.

Descriptive statistics of the participant-reported and clinical outcomes will be produced, as appropriate for each measure for each group at all timepoints. Changes, where appropriate, between baseline and 6-months will be summarised descriptively and presented by allocated group. Interval estimates of the potential intervention effect of FIT+TAU, relative to TAU only, will be produced, with the promise of the FIT intervention (as per section 4.1, objective 2) assessed using the confidence interval for the between-group difference in change in grams of pure alcohol consumed in previous week (proposed primary outcome for definitive trial).

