17.5. Participant population

As described above, the primary descriptive comparative analyses of the participant-reported and other clinical outcomes will be on an intention-to-treat basis, including all the outcome data obtained from all participants, with participants analysed in the group to which they were originally allocated. Safety data (SAEs and SARs) will be presented on a per-protocol basis.

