4.2 ANALYSIS POPULATIONS

Primary analysis (in the form of summary statistics such as means and standard deviations (SDs) or medians and interquartile ranges (IQR), where appropriate), will be undertaken on an Intention To Treat (ITT) basis, where participants are analysed according to their allocated group, regardless of adherence to the protocol or lack of participation or completion of FIT sessions if allocated to the intervention group. No formal (i.e. no hypothesis testing/inferential) analysis will be performed. Missing responses will be imputed according to the guidance set out in section 4.8.1. Any participants with non-imputable items/scores, will not be included in the ITT analysis for the outcome/time-point under consideration. We will present summary statistics of outcomes for participants who complete all visits in both groups. the changes between baseline and each of the 28, 90, and 180 day assessments, a participant will need to have non-missing or imputable data at both of the time points to be included in the analysis. Kaplan-Meier survivor curves will be used to characterise the time of relapse to alcohol use by group.

The safety population will include all participants who consent to participate in the study, with safety data collected from the time of recruitment until a participant completes or withdraws from the study. Any participant who does not attend at least one FIT session will be analysed as TAU and any participant who has received at least one FIT session will be analysed as TAU + FIT.

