Fibrosis			
Cirrhosis			
Child-Pugh Score			
Mean (SD) [range]			
Median (IQR)			
MELD Score			
Mean (SD) [range]			
Median (IQR)			

*Participants can provide data in more than one category – percentages will not necessarily add to 100%

Table 10: Summary statistics for the proposed primary and secondary outcome measures by allocated group

Variable	Time point	TAU			FIT + TAU		
		N	Mean (SD) (95% CI)/Median [IQR]	Range	N	Mean (SD) (95% CI) /Median [IQR]	Range
Alcohol Use (grams of pure alcohol/ week)	baseline						
	28 (±7) days						
	90 (±7) days						
	180 (±14) days						
SADQ Score	baseline						
	28 (±7) days						
	90 (±7) days						
	180 (±14) days						
WEMWBS	baseline						
	28 (±7) days						
	90 (±7) days						
	180 (±14) days						
SWEMWBS	baseline						
	28 (±7) days						
	90 (±7) days						
	180 (±14) days						
Ethyl Glucuronide (µg/L)	180 (±14) days						
Ethyl Sulphate (µg/L)	180 (±14) days						
Re- hospitalisation*	180 (±14) days						

* Rates and corresponding confidence intervals given for re-hospitalisation

Table 11: Summary statistics for the changes between baseline and 28, 90, and 180 day assessments for proposed primary and secondary outcomes including only those participants who complete all follow-up visits

Variable	Time point	TAU			FIT + TAU		
		N	Mean (SD) Change From Baseline (95% CI)/Median [IQR]	Range	N	Mean (SD) Change From Baseline (95% CI) /Median [IQR]	Range
Alcohol Use (grams of pure alcohol/ week)	28 (±7) days						
	90 (±7) days						
	180 (±14) days						
SADQ Score	28 (±7) days						
	90 (±7) days						
	180 (±14) days						
WEMWBS	28 (±7) days						
	90 (±7) days						
	180 (±14) days						
SWEMWBS	28 (±7) days						
	90 (±7) days						
	180 (±14) days						

Table 11b: Proportion of participants who completed TLFB assessment and with no alcohol consumption as calculated from TLFB

Variable	Time point	TAU	FIT + TAU
		N (% of participants with complete TLFB)	N (% of participants with complete TLFB)
Participants with zero alcohol consumption	Baseline		
	28 (±7) days		
	90 (±7) days		
	180 (±14) days		

Table 12: Re-hospitalisations by allocated group

Re-hospitalisation	TAU N (%)				FIT + TAU N (%)			
	0	1	2	>2	0	1	2	>2
No. of re-admissions								
By 28 (± 7) days								
By 90 (± 7) days								
By 180 (± 14) days								

Table 13: Proportion of participants who relapse and time to relapse to alcohol use by allocated group

	TAU	FIT + TAU
N (%) who relapsed by:		
28 (± 7) days		

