90 (± 7) days		
180 (± 14) days		
Time to relapse (days)	Median (Inter-quartile Range) [Range]	Median (Inter-quartile Range) [Range]

Table 14: Unadjusted between-group differences and confidence intervals for proposed primary and secondary outcome measures, with unadjusted confidence intervals

Variable	Time Point	Mean Between-group Difference	Unadjusted 95% CI	Unadjusted 85% CI	Unadjusted 75% CI
Alcohol Use (grams of pure alcohol/ week)	28 (± 7) days				
	90 (± 7) days				
	180 (± 14) days				
SADQ Score	28 (± 7) days				
	90 (± 7) days				
	180 (± 14) days				
WEMWBS	28 (± 7) days				
	90 (± 7) days				
	180 (± 14) days				
SWEMWBS	28 (± 7) days				
	90 (± 7) days				
	180 (± 14) days				
Ethyl Glucuronide ($\mu\text{g/L}$)	180 (± 14) days				
Ethyl Sulphate ($\mu\text{g/L}$)	180 (± 14) days				
Re-hospitalisation*	180 (± 14) days				

* Rates and corresponding confidence intervals given for re-hospitalisation

Table 15: Between-group differences and confidence intervals for proposed primary and secondary outcome measures, adjusted for stratification variables (dichotomised baseline SADQ score and site)

Variable	Time Point	Adjusted Mean Between-group Difference	Adjusted 95% CI	Adjusted 85% CI	Adjusted 75% CI
Alcohol Use (grams of pure alcohol/ week)	28 (± 7) days				
	90 (± 7) days				
	180 (± 14) days				
SADQ Score	28 (± 7) days				
	90 (± 7) days				
	180 (± 14) days				
WEMWBS	28 (± 7) days				
	90 (± 7) days				
	180 (± 14) days				
SWEMWBS	28 (± 7) days				
	90 (± 7) days				
	180 (± 14) days				
Ethyl Glucuronide ($\mu\text{g/L}$)	180 (± 14) days				
Ethyl Sulphate ($\mu\text{g/L}$)	180 (± 14) days				
Re-hospitalisation*	180 (± 14) days				

* Rates and corresponding confidence intervals given for re-hospitalisation

Table 16: Unadjusted between-group differences and confidence intervals of change from baseline for proposed primary and secondary outcomes

Variable	Time Point	Mean Between-group Difference of Change From Baseline	Unadjusted 95% CI	Unadjusted 85% CI	Unadjusted 75% CI
Alcohol Use(grams of pure alcohol/ week)	28 (± 7) days				
	90 (± 7) days				
	180 (± 14) days				
SADQ Score	28 (± 7) days				
	90 (± 7) days				
	180 (± 14) days				
WEMWBS	28 (± 7) days				
	90 (± 7) days				
	180 (± 14) days				
SWEMWBS	28 (± 7) days				
	90 (± 7) days				
	180 (± 14) days				
Ethyl Glucuronide ($\mu\text{g/L}$)	180 (± 14) days				
Ethyl Sulphate ($\mu\text{g/L}$)	180 (± 14) days				

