Table 17: Between-group differences and confidence intervals for of change from baseline for proposed primary and secondary outcome measures, adjusted for stratification variables (dichotomised baseline SADQ score and site)

Variable	Time Point	Adjusted Mean Between-group Difference of Change From Baseline	Adjusted 95% CI	Adjusted 85% CI	Adjusted 75% CI
Alcohol Use (grams of pure alcohol/ week)	28 (± 7) days				
	90 (± 7) days				
	180 (± 14) days				
SADQ Score	28 (± 7) days				
	90 (± 7) days				
	180 (± 14) days				
WEMWBS	28 (± 7) days				
	90 (± 7) days				
	180 (± 14) days				
SWEMWBS	28 (± 7) days				
	90 (± 7) days				
	180 (± 14) days				
Ethyl Glucuronide ($\mu\text{g/L}$)	180 (± 14) days				
Ethyl Sulphate ($\mu\text{g/L}$)	180 (± 14) days				

Table 18: Estimates of standard deviations of proposed primary outcome (alcohol use) for informing sample size calculations for a definitive trial

Parameter	Point Estimate	80% CI*	90% CI*
Standard deviation of alcohol use at baseline			
Standard deviation of alcohol use at 180 (± 14) days assessment			
Standard deviation of change in alcohol use between baseline and 180 (± 14) days assessment			

* upper bound of two-sided confidence interval relevant as conservative estimate for sample size calculations

Table 19: Estimates of correlation coefficients for proposed primary outcome (alcohol use) for informing sample size calculations for a definitive trial

Parameter	Point Estimate	80% CI*	90% CI*
Correlation coefficient between baseline and 180 (± 14) days assessment of alcohol use			
Correlation coefficient between baseline and change between baseline and 180 (± 14) days assessment of alcohol use			

* lower bound of two-sided confidence interval relevant as conservative estimate for sample size calculations

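### Table 11, the only shell showing change from baseline by arm, is limited to all-visit completers, contrary to Protocol 17.5 and to the SAP's own rules in 4.2 and 5.3

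*SAP*

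**What the plan says.** Two places restrict the population. The Table 11 title in SAP Appendix A covers change at days 28, 90 and 180, "including only those participants who complete all follow-up visits". SAP 4.2 states: "We will present summary statistics of outcomes for participants who complete all visits in both groups". The SAP revision log lists wording of this kind for Section 4.2 among changes made after database lock and data export, with the statisticians unblinded, and describes it as applying only if needed. The log does not mention the Table 11 title, so the date of that title is unknown.

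Three places include everyone with data. Protocol 17.5 defines the intention-to-treat analysis as "including all the outcome data obtained from all participants". The same SAP 4.2 paragraph requires usable data only at the two time points that form a change score; that sentence has lost its opening words. SAP 5.3 plans means and confidence intervals of change by allocated group, with no completer limit.

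The neighbouring shells carry no limit either. The second table numbered 10 ("Summary statistics for the proposed primary and secondary outcome measures by allocated group") gives levels by arm. Table 16 ("Unadjusted between-group differences and confidence intervals of change from baseline for proposed primary and secondary outcomes") and Table 17 give differences between arms. None of them gives change by arm.

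Two related items:

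- Table 11b, on zero consumption, heads its columns "N (% of participants with complete TLFB".
- Protocol 17.4 promises: "Individuals lost to follow-up will be compared to those who complete the pilot study to identify any potential bias". SAP 5.1.2 covers the reasons for and extent of loss, and SAP 4.7 the pattern of missing data, but neither specifies that comparison.

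**The concern.** Under the Table 11 title, a participant with valid alcohol data at baseline and day 180 is left out of the day-180 change because of a missed telephone call at day 28 or day 90. That discards data on the proposed primary outcome which Protocol 17.5 says will be used. Protocol 10.6 makes the case realistic: after failed contact attempts the site waits until the next scheduled visit, so a missed contact does not end follow-up.

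Three things are at stake. The by-arm display of the key outcome may rest on fewer people than the plan expects. Its arm means may disagree with the between-arm differences printed elsewhere in the report. If attendance is related to drinking, the restricted display may also misrepresent both arms. A population rule introduced after lock by unblinded statisticians is a weak basis for the only table of its kind.

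**Working it through.** **1. The plan's own figure.** Protocol 17.1 and SAP 3.5 give 90 participants and 75% retention at six months. Allocation is 1:1, so there are 45 per arm. 45 × 0.75 = 33.75, rounded down to 33 per arm. The stated minimum of 33 is reproduced.

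**2. Day-180 numbers under each rule.** With the two-time-point rule, day-180 change is available for about 33 per arm, taking baseline as complete. With the all-visit rule it is 45 × P(attended all three visits). The documents give no retention for days 28 and 90, so those values are assumptions:

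| Attendance at days 28 / 90 / 180 | Lowest possible: sum − 2 | Independent: product | Highest possible: minimum |
|---|---|---|---|
| 90% / 80% / 75% | 0.45 × 45 = 20.3 | 0.54 × 45 = 24.3 | 0.75 × 45 = 33.75 |
| 75% / 75% / 75% | 0.25 × 45 = 11.3 | 0.422 × 45 = 19.0 | 0.75 × 45 = 33.75 |

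The all-visit number is thus about 24 per arm in the first case (range 20 to 33) and about 19 in the second (range 11 to 33).

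**3. Monotone dropout.** If nobody returns after a missed visit, everyone seen at day 180 attended all visits, and the day-180 row loses nobody. The earlier rows still lose people. At 90%, 80% and 75%, day 28 falls from 45 × 0.90 = 40.5 to 33.75 per arm, and day 90 from 45 × 0.80 = 36 to 33.75.

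**4. Reconciliation.** If Table 11 uses all-visit completers and Tables 16 and 17 use everyone with two time points, subtracting the Table 11 arm means need not give the Table 16 difference. They must agree only when the two sets of participants coincide.

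**5. Direction of any selection.** Let a be the share abstinent among those seen at day 180, and qa and qd the chances that abstainers and drinkers attended both earlier visits. The abstinent share among all-visit completers is a·qa / [a·qa + (1 − a)·qd]. With a = 1/3 (assumed):

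- qa = qd: 33%, unchanged.
- qa = 0.9, qd = 0.6: 0.30 / (0.30 + 0.40) = 43%.
- qa = 0.6, qd = 0.9: 0.20 / (0.20 + 0.60) = 25%.

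The sign depends on an attendance pattern that the documents do not give. This step shows only that the direction is open; Table 11 reports change scores, not abstinence.

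**6. Table 11b.** Read complete timeline follow-back as all seven days recorded. Let Z be the participants with seven recorded days and no drinking, C all those with seven recorded days, and D those with at least one missing day and at least one recorded drinking day. The shell gives Z / C. Members of D are known not to be abstinent, so counting them gives Z / (C + D), which cannot exceed Z / C. The shell's rule can therefore only raise the percentage. Table 9b provides for day-level gaps, including days the participant could not remember, so D need not be empty.

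**The case against.** The strongest reply is that little depends on Table 11. Appendix A presents its tables as examples, and SAP 5.3 already commits to by-arm change without a completer limit. Protocol 17.4 judges the promise of FIT from the confidence interval for the between-group difference in change. The shells for that difference, Tables 16 and 17, state no restriction. Nor do the by-arm levels or the standard deviations and correlations in Tables 18 and 19, and the progression criteria in SAP 5.5 do not use Table 11. The trial tests no hypotheses, and the revision log makes the completer summary conditional. Table 9b already reports timeline follow-back completeness by day, arm and reason.

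Most of this stands, and it limits the consequence. It does not remove the contradiction. SAP 4.2 is plan text rather than an example, and its completer sentence is unconditional as it now reads. SAP 5.3 has no unrestricted shell to carry its by-arm change. Reporting completeness in Table 9b does not correct the denominator in Table 11b.

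A reader might go further and infer that the all-visit rule selects abstainers and makes both arms look better. No passage links missed visits to drinking, and step 5 shows that the shift can go either way or be nil. A reader might also take the SAP 4.2 sentence to govern the effect estimates. Its scope is unclear beside the broken sentence, but the titles of Tables 16 and 17 do not support that reading.

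**Conclusion.** The SAP contradicts both the protocol and itself on who enters the by-arm summary of change. This follows from the text and needs no assumption.

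The cost in numbers at day 180 runs from none, if dropout is monotone, to about 9 of 33 per arm (33 − 24) under independent attendance of 90%, 80% and 75%. The figures for days 28 and 90, and independence, are assumptions. Rows for earlier visits lose people even under monotone dropout.

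Failure to reconcile with Tables 16 and 17 is a likely practical result whenever the two populations differ. Bias in the by-arm changes is possible if missing a visit is related to drinking, but it is not demonstrated in direction or size. The between-group estimates and progression criteria are not shown to be affected. Only the SAP 4.2 wording can be placed after database lock; the Table 11 title cannot.

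The Table 11b point is separate. The direction of its effect is certain, and its size depends on how many participants have both a missing day and a recorded drinking day. The absent comparison of lost and retained participants is an omission against Protocol 17.4 and does not add to the Table 11 problem.

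**What to change.** - Remove the completer restriction from SAP 4.2 and from the Table 11 title, and repair the incomplete sentence in SAP 4.2.
- Summarise by-arm change in every participant with usable data at baseline and the visit concerned, and show N for each row.
- If the all-visit subset is wanted, keep it only as a sensitivity table, labelled as specified after database lock.
- In Table 11b, count any recorded drinking day as not abstinent even when other days are missing. Report separately those with missing days and no recorded drinking, whose status is unknown.
- Add the comparison of lost and retained participants promised in Protocol 17.4.

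The cost is SAP wording and rerunning a few descriptive tables on data already held. N will differ between rows, which a footnote can explain.
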